 Women of childbearing potential require a negative pregnancy test prior to starting treatment; sexually active patients must use two effective methods of birth control- including a medically accepted barrier method of contraceptive method (e.g., male or female condom). Abstinence is an acceptable method of birth control. Pregnancy testing is required prior to tumor imaging per institutional guidelines.

 If patients develop Grade 4 neutropenia then CBCs should be checked every 3 to 4 days until recovery to Grade 3

 Tumor Disease Evaluation should be obtained on the next consecutive cycle after initial documentation

THIS PROTOCOL IS FOR RESEARCH PURPOSES ONLY, SEE PAGE 1 FOR USAGE POLICY

- of either a PR or CR. Please note that for solid tumor patients, if the institutional investigator determines that the patient has progressed based on clinical or laboratory evidence, he/she may opt not to confirm this finding radiographically.
- 4 Patient diary (see [Appendix VII](#)) should be reviewed and uploaded into RAVE weekly during Cycle 1, and after completion of each treatment cycle.
  - 5 See [Section 8.3](#) for timing of PK studies.
  - 6 In consenting patients. See [Section 8.4](#) for timing of Pharmacodynamic studies.
  - 7 See [Section 8.5](#) for details of tissue studies.
  - 8 Part C: Observations are required as scheduled during protocol treatment only; *i.e.* weekly labs and observations are not required during the “surgery window” and may be held until resuming protocol therapy.
  - 9 Patients in Part C who interrupt treatment of Cycle 1 due to required resection should have scans repeated prior to resuming protocol therapy.
  - 10 Snellen eye chart should be used to assess visual acuity. If a decline in visual acuity occurs or other visual symptoms occur, the patient should be referred to an ophthalmologist for an examination.

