**10.0 CRITERIA FOR REMOVAL FROM PROTOCOL THERAPY AND OFF STUDY CRITERIA**

**10.1 Criteria for Removal from Protocol Therapy**

- a) Clinical (including physical examination or serum tumor markers) or radiographic evidence of progressive disease (See [Section 12.0](#)).

THIS PROTOCOL IS FOR RESEARCH PURPOSES ONLY, SEE PAGE 1 FOR USAGE POLICY

- b) Adverse Events requiring removal from protocol therapy (See [Section 6.0](#)).
- c) Refusal of further protocol therapy by patient/parent/guardian
- d) Non-compliance that in the opinion of the investigator does not allow for ongoing participation.
- e) Completion of 24 cycles
- f) Physician determines it is not in the patient's best interest.
- g) Repeated eligibility laboratory studies (CBC with differential, bilirubin, ALT (SGPT) or serum creatinine) are outside the parameters required for eligibility prior to the start of selinexor (See [Section 8.1](#)).
- h) Failure to adequately recover from surgery within 6 weeks after surgery (patients in Part C)
- i) Study is terminated by Sponsor.
- j) Pregnancy

**Patients who are removed from protocol therapy during cycle 1 should continue to have the required observations in [Section 8.1](#) until the originally planned end of the cycle or until all adverse events have resolved per [Section 13.4.4](#), whichever happens LATER. The only exception is with documentation of the patient's withdrawal of consent. Patients who are removed from protocol therapy in subsequent cycles should have the necessary observations to ensure adequate clinical care.**

Patients who are off protocol therapy are to be followed until they meet the criteria for Off Study (see below). Ongoing adverse events, or adverse events that emerge after the patient is removed from protocol therapy, but within 30 days of the last dose of investigational agent, must be followed and reported via RAVE and CTEP-AERS (if applicable). Follow-up data will be required unless consent is withdrawn.

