### 12.2.1 Definitions

12.2.1.1 Evaluable for objective response: Patients who exhibit objective disease progression prior to the end of cycle 1 will be considered evaluable for response. For all other patients, only those patients who have measurable disease present at baseline, have received at least one cycle of therapy, and have had their disease re-evaluated will be considered evaluable for response.

12.2.1.2 Evaluable Non-Target Disease Response: Patients who have lesions present at baseline that are evaluable but do not meet the definitions of measurable disease, have received at least one cycle of therapy, and have had their disease re-evaluated will be considered evaluable for non-target disease. The response assessment is based on the presence, absence, or unequivocal progression of the lesions.

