## 12.7 Best Response

### 12.7.1 Evaluation of Best Overall Response

The best overall response is the best response recorded from the start of the treatment until disease progression/recurrence (taking as reference for progressive disease the smallest measurements recorded since the treatment started). The patient's best response assignment will depend on the achievement of both measurement and confirmation criteria.

Table 1: For Patients with Measurable Disease (i.e., Target Disease)

Target Lesions	Non-Target Lesions	New Lesions	Overall Response	Best Overall Response when Confirmation is Required*
CR	CR	No	CR	≥28 days Confirmation**
CR	Non-CR/Non-PD	No	PR	≥28 days Confirmation**
CR	Not evaluated	No	PR	
PR	Non-CR/Non-PD/not evaluated	No	PR	
SD	Non-CR/Non-PD/not evaluated	No	SD	documented at least once ≥28 days from baseline**
PD	Any	Yes or No	PD	no prior SD, PR or CR
Any	PD***	Yes or No	PD	
Any	Any	Yes	PD	

\* See RECIST 1.1 manuscript for further details on what is evidence of a new lesion.  
 \*\* Only for non-randomized trials with response as primary endpoint.  
 \*\*\* In exceptional circumstances, unequivocal progression in non-target lesions may be accepted as disease progression.  
 Note: Patients with a global deterioration of health status requiring discontinuation of treatment without objective evidence of disease progression at that time should be reported as “symptomatic deterioration.” Every effort should be made to document the objective progression even after discontinuation of treatment.

Table 2: For Patients with Non-Measurable Disease (i.e., Non-Target Disease)

Non-Target Lesions	New Lesions	Overall Response
CR	No	CR
Non-CR/non-PD	No	Non-CR/non-PD*
Not all evaluated	No	not evaluated
Unequivocal PD	Yes or No	PD
Any	Yes	PD

\* 'Non-CR/non-PD' is preferred over 'stable disease' for non-target disease since SD is increasingly used as an endpoint for assessment of efficacy in some trials so to assign this category when no lesions can be measured is not advised

Table 3. Sequences of overall response assessments with corresponding best response.

1 st Assessment	2 nd Assessment	Best Response
Progression		Progressive disease
Stable, PR, CR	Progression	Progressive disease
Stable	Stable	Stable
Stable	PR, CR	Stable
Stable	Not done	Not RECIST classifiable
PR	PR	PR
PR	CR	PR
PR, CR	Not done	Not RECIST classifiable
CR	CR	CR

Table 4: Overall Response for Patients with Neuroblastoma and Measurable Disease

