### 12.7.2 Duration of Response

Duration of overall response: The duration of overall response is measured from the time measurement criteria are met for CR, PR, or MR (whichever is first recorded) until the first date that recurrent or progressive disease is objectively documented (taking as reference for progressive disease the smallest measurements recorded since the treatment started).

The duration of overall CR is measured from the time measurement criteria are first met for CR until the first date that progressive disease is objectively documented.

Duration of stable disease: Stable disease is measured from the start of the treatment until the criteria for progression are met, taking as reference the smallest measurements recorded since the treatment started, including the baseline measurements.

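### In Part A, measurable solid-tumor patients who fail clinically or die in Cycle 1 without objective progression drop out of the response denominator, which biases the descriptive response rate upward.

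*Combined protocol and SAP*

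**What the plan says.** **Stopping.** Section 10.1(a) removes a patient on "Clinical (including physical examination or serum tumor markers) or radiographic evidence of progressive disease". Footnote 3 of the 8.1 table adds that a solid-tumor patient whom the investigator judges "has progressed based on clinical or laboratory evidence, he/she may opt not to confirm this finding radiographically".

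**Entering the response denominator.** Section 12.2.1.1 has two routes. The first is for early failures: "Patients who exhibit objective disease progression prior to the end of cycle 1 will be considered evaluable for response". The second is for everyone else: of patients with measurable disease at baseline, only those who "have received at least one cycle of therapy, and have had their disease re-evaluated will be considered evaluable for response". Death is not mentioned.

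**Best response.** For measurable solid tumors, 12.2.4 defines progression by target-lesion sums, new lesions or unequivocal non-target progression. There is no clinical route. The Note to Table 1 in 12.7.1 introduces the label symptomatic deterioration: any "global deterioration of health status requiring discontinuation of treatment without objective evidence of disease progression at that time should be reported as" such. The Note then adds: "Every effort should be made to document the objective progression even after discontinuation of treatment". Table 3 classes stable disease or response followed by *Progression* as progressive disease, and the same followed by *Not done* as not RECIST classifiable.

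**Duration.** Under 12.7.2 a response lasts "until the first date that recurrent or progressive disease is objectively documented". The stable-disease sentence refers to the criteria for progression and does not use the word objectively.

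**The concern.** The event that ends treatment and the event that the response analysis recognises are not the same. A patient whose disease worsens so quickly that therapy stops on clinical grounds in Cycle 1 is a treatment failure on any reading. Under 12.2.1.1 that patient may nevertheless be neither a responder nor a non-responder, but simply not evaluable. The exclusion depends on outcome: it removes early failures and cannot remove a confirmed responder, so the bias has one direction.

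What is at stake is the preliminary estimate of antitumor effect in Part A (aim 1.2.1). Section 11.5 reports it descriptively with no decision threshold, so the rate and its denominator are all the reader has. The protocol already deals with the problem in two other places, which suggests an oversight here and not a deliberate choice.

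**Working it through.** **1. Plan's own figures.** The only quantified response rule is the one for Part B in 11.1. At a true rate of 20%, P(at least 1 response in 10) = 1 - 0.80^10 = 0.893. At 5%, 1 - 0.95^10 = 0.401. Both match the stated 89.3% and 40.1%. Neither depends on 12.2.1.1, because Part B has its own evaluability rule in 11.2.3. No stated figure attaches to the Part A response rate.

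**2. Tracing Part A patients with measurable solid tumors through the rules.** Receiving at least one cycle is read here as completing Cycle 1.

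| Patient | 12.2.1.1 | Result |
|---|---|---|
| Cycle 1 clinical or laboratory progression, no scan | No objective progression, no re-evaluation | Not evaluable |
| Cycle 1 clinical stop, scanned at the planned cycle end, no objective PD | Re-evaluated, but less than one cycle received | Not evaluable |
| Death in Cycle 1, no objective progression documented | Neither route met | Not evaluable |
| Cycle 1 stop, objective PD by scan or caliper measurement | First route met | Evaluable, PD |
| Stable at the end-of-Cycle-1 scan, later clinical stop without a scan | Second route met | Evaluable, but Table 3 class unclear |

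For the last row, Table 3 gives progressive disease if the investigator's judgment is entered as *Progression*, and not RECIST classifiable if the second assessment is entered as *Not done*. The text does not say which applies, or whether an unclassifiable patient stays in the denominator.

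**3. Comparison within the protocol.** In Part B, 11.2.3 makes progression or death on therapy sufficient for evaluability, without requiring that progression be objective, and counts every patient without a centrally confirmed response as a non-responder. For solid tumors with evaluable but not measurable disease, 12.3.5 includes clinical and laboratory progression in the definition of PD. Part A measurable solid tumors have neither provision.

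**4. Size (illustration only).** If k early failures are dropped from N treated patients with R responders, the reported rate is R/(N-k) in place of R/N, an inflation of N/(N-k). The documents give no k and no R. Assume R = 2 and N = 24, taking N from the Amendment #4 base case in 11.1: 3 levels x 6 + 6 PK patients = 24, and 24/0.8 = 30 with inevaluability. The intervals are exact (Clopper-Pearson).

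| k | Rate | 95% CI | Inflation |
|---|---|---|---|
| 0 | 2/24 = 8.3% | 1.0 to 27.0% | 1.00 |
| 2 | 2/22 = 9.1% | 1.1 to 29.2% | 24/22 = 1.09 |
| 4 | 2/20 = 10.0% | 1.2 to 31.7% | 24/20 = 1.20 |
| 6 | 2/18 = 11.1% | 1.4 to 34.7% | 24/18 = 1.33 |

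**The case against.** **Cycle 1 is partly covered elsewhere.** Section 10.1 asks that patients removed in Cycle 1 keep the 8.1 observations at least until the planned end of the cycle, and those include the end-of-Cycle-1 tumor evaluation. In the 8.1 table the marker for footnote 3 sits on the later-cycle evaluations, although its wording is general. This stands in part: some scans will be recovered. It does not rescue a patient who dies, or one scanned without objective PD after less than a full cycle.

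**The labels need not coincide.** A reader might infer that every solid-tumor patient who stops clinically is progressive in 10.1, symptomatic deterioration in 12.7.1 and not evaluable in 12.2.1.1 all at once. The documents do not support that. Section 10.1 is a removal rule, and the Note covers global health deterioration, not a marker rise or growth on examination. Section 12.2.1.1 bites only before the first re-evaluation. Caliper-measured lesions can show objective progression without a scan (12.2.3.1), and evaluable-only disease falls under 12.3.5.

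**Durations.** A reader might also infer that a response or stable disease ended clinically never gets an end date. That goes too far. The Note asks for objective progression to be sought after stopping, and a later date closes the interval. The stable-disease sentence is not worded as objective. Later documentation may be missing, since patients go off study 30 days after the last dose (10.2). But no time-to-event analysis is planned, so a charge of informative censoring has no target. Ending response on a clinical date would exchange an objective standard for a subjective one; that is a trade-off and not a correction.

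**The illustration is soft.** This stands. The 24 is already net of inevaluable patients and includes CNS tumors and evaluable-only disease. Also, 11.2.1 replaces patients who miss Cycle 1 doses because of progression, so the toxicity set and the response set differ.

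**Conclusion.** The point holds for Part A patients with measurable solid tumors. As written, 12.2.1.1 excludes patients who die, or are removed for clinical or laboratory progression, in Cycle 1 without objective PD and without a completed cycle and re-evaluation. The bias in the response rate can only be upward. After the first scan the defect is different: such patients are evaluable, but Table 3 leaves their class and their place in the denominator open.

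The size is N/(N-k). On the assumed numbers above that is 1.09 to 1.33, or 8.3% reported as 9.1% to 11.1%, well inside the interval of 1.0 to 27.0%. The true k is unknown and would be reduced by scans obtained under 10.1. The analysis is exploratory and carries no Part A threshold. The Part B rule, evaluable-only disease under 12.3.5, the Part C endpoint and the MTD are not affected. It is worth correcting because it is systematic, cheap to remove and at odds with 11.2.3.

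**What to change.** - **12.2.1.1 and the Note in 12.7.1:** state that any treated Part A patient with measurable disease at baseline who is removed for clinical or laboratory progression, or who dies on therapy, before objective re-evaluation is counted as a non-responder and stays in the denominator, in line with 11.2.3.
- **Table 3:** state how clinical progression without a scan is entered after a first assessment, and that the patient remains in the denominator.
- **Reporting:** keep symptomatic deterioration as a recorded reason and give the number of patients so classified.
- **12.7.2:** keep the objective end point for response duration, and report how many responses ended clinically without objective documentation.

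Cost: two or three sentences and a slightly less favourable reported rate. No additional scans or data are needed, and no rule for stopping treatment changes.

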### 12.7.2 Duration of Response

Duration of overall response: The duration of overall response is measured from the time measurement criteria are met for CR, PR, or MR (whichever is first recorded) until the first date that recurrent or progressive disease is objectively documented (taking as reference for progressive disease the smallest measurements recorded since the treatment started).

The duration of overall CR is measured from the time measurement criteria are first met for CR until the first date that progressive disease is objectively documented.

Duration of stable disease: Stable disease is measured from the start of the treatment until the criteria for progression are met, taking as reference the smallest measurements recorded since the treatment started, including the baseline measurements.

## 13.0 ADVERSE EVENT REPORTING REQUIREMENTS

Adverse event data collection and reporting which are required as part of every clinical trial, are done to ensure the safety of patients enrolled in the studies as well as those who will enroll in future studies using similar agents. Adverse events are reported in a routine manner at scheduled times during a trial. (Please follow directions for routine reporting provided in the data collection packet for this protocol). Additionally, certain adverse events must be reported in an expedited manner to allow for optimal monitoring of patient safety and care. The following sections provide information about expedited reporting.

Reporting requirements may include the following considerations: 1) whether the patient has received an investigational or commercial agent; 2) whether the adverse event is considered serious; 3) the grade (severity); and 4) whether or not hospitalization or prolongation of hospitalization was associated with the event.

An investigational agent is a protocol drug administered under an Investigational New Drug Application (IND). In some instances, the investigational agent may be available commercially, but is actually being tested for indications not included in the approved package label.

Commercial agents are those agents not provided under an IND but obtained instead from a commercial source. The NCI, rather than a commercial distributor, may on some occasions distribute commercial agents for a trial.

### 13.1 Steps to Determine If an Adverse Event Is To Be Reported In an Expedited Manner

Step 1: Identify the type of adverse event using the NCI CTCAE version 5.0. All appropriate treatment areas should have access to a copy of the CTCAE version 5.0. A copy of the CTCAE version 5.0 can be downloaded from the CTEP website ([http://ctep.cancer.gov/protocolDevelopment/electronic\\_applications/ctc.htm](http://ctep.cancer.gov/protocolDevelopment/electronic_applications/ctc.htm)).

THIS PROTOCOL IS FOR RESEARCH PURPOSES ONLY, SEE PAGE 1 FOR USAGE POLICY

**Step 2:** Grade the adverse event using the NCI CTCAE.

**Step 3:** Review Table A in this section to determine if:

- the adverse event is considered serious;
- there are any protocol-specific requirements for expedited reporting of specific adverse events that require special monitoring; and/or
- there are any protocol-specific exceptions to the reporting requirements.

**Note:** This includes all events that occur within 30 days of the last dose of protocol treatment. Any event that occurs more than 30 days after the last dose of treatment and is attributed (possibly, probably, or definitely) to the agent(s) must also be reported according to the instructions in the table below. Attribution categories are as follows: Unrelated, Unlikely, Possible, Probable, and Definite.

**Table A: Phase 1 and Early Phase 2 Studies: Expedited Reporting Requirements for Adverse Events that Occur on Studies under an IND/IDE within 30 Days of the Last Administration of the Investigational Agent/Intervention**


FDA REPORTING REQUIREMENTS FOR SERIOUS ADVERSE EVENTS (21 CFR Part 312)  NOTE: Investigators MUST immediately report to the sponsor ANY Serious Adverse Events, whether or not they are considered related to the investigational agent(s)/intervention (21 CFR 312.64)                  An adverse event is considered serious if it results in ANY of the following outcomes:
 
 
1) Death
 
2) A life-threatening adverse event
 
3) An adverse event that results in inpatient hospitalization or prolongation of existing hospitalization for <math>\geq 24</math> hours
 
4) A persistent or significant incapacity or substantial disruption of the ability to conduct normal life functions
 
5) A congenital anomaly/birth defect.
 
6) Important Medical Events (IME) that may not result in death, be life threatening, or require hospitalization may be considered serious when, based upon medical judgment, they may jeopardize the patient or subject and may require medical or surgical intervention to prevent one of the outcomes listed in this definition. (FDA, 21 CFR 312.32; ICH E2A and ICH E6).
 
		

ALL SERIOUS adverse events that meet the above criteria MUST be immediately reported via CTEP-AERS within the timeframes detailed in the table below.
		
Hospitalization	Grade 1 and Grade 2 Timeframes	Grade 3-5 Timeframes
Resulting in Hospitalization $\geq 24$ hrs	7 Calendar Days	24-Hour 5 Calendar Days
Not resulting in Hospitalization $\geq 24$ hrs	Not required	

Expedited AE reporting timelines are defined as:
 
 
○ “24-Hour; 5 Calendar Days” - The AE must initially be reported via CTEP-AERS within 24 hours of learning of the AE, followed by a complete expedited report within 5 calendar days of the initial 24-hour report.
 
○ “7 Calendar Days” - A complete expedited report on the AE must be submitted within 7 calendar days of learning of the AE.
 
		

Serious adverse events that occur more than 30 days after the last administration of investigational agent/intervention and have an attribution of possible, probable, or definite require reporting as follows:  Expedited 24-hour notification followed by complete report within 5 calendar days for:
		

- All Grade 3, 4, and Grade 5 AEs

**Expedited 7 calendar day reports for:**

- Grade 2 AEs resulting in hospitalization or prolongation of hospitalization

 For studies using PET or SPECT IND agents, the AE reporting period is limited to 10 radioactive half-lives, rounded UP to the nearest whole day, after the agent/intervention was last administered. Footnote "1" above applies after this reporting period.

Effective Date: May 5, 2011

- Any medical event equivalent to CTCAE grade 3, 4, or 5 that precipitates hospitalization (or prolongation of existing hospitalization) must be reported regardless of attribution and designation as expected or unexpected with the exception of any events identified as protocol-specific expedited adverse event reporting exclusions.
- Any event that results in persistent or significant disabilities/incapacities, congenital anomalies, or birth defects must be reported via CTEP-AERS if the event occurs following treatment with an agent under a CTEP IND.
- Use the NCI protocol number and the protocol-specific patient ID provided during trial registration on all reports.

Additional Instructions or Exceptions to CTEP-AERS Expedited Reporting Requirements for Phase 1 Trials Utilizing an Agent under a CTEP-IND or Non-CTEP IND:

- Any death that occurs more than 30 days after the last dose of treatment with an investigational agent which can be attributed (possibly, probably, or definitely) to the agent and is not clearly due to progressive disease must be reported via CTEP-AERS for an agent under a CTEP or non-CTEP IND agent per the timelines outlined in the table above.
- Myelosuppression, (Grade 1 through Grade 4 adverse events as defined in the table below), does not require expedited reporting, unless it is associated with hospitalization.

Category	Adverse Events
INVESTIGATIONS	Platelet count decreased
INVESTIGATIONS	White blood cell decreased
INVESTIGATIONS	Neutrophil count decreased
INVESTIGATIONS	Lymphocyte count decreased
BLOOD AND LYMPHATIC SYSTEM DISORDERS	Anemia

- Grade 1 and 2 adverse events listed in the table below do **not** require expedited reporting via CTEP-AERS:

Category	Adverse Events
BLOOD AND LYMPHATIC SYSTEM DISORDERS	Febrile neutropenia
EYE DISORDERS	Blurred vision
GASTROINTESTINAL DISORDERS	Constipation
GASTROINTESTINAL DISORDERS	Diarrhea
GASTROINTESTINAL DISORDERS	Dry mouth
GASTROINTESTINAL DISORDERS	Abdominal pain
GASTROINTESTINAL DISORDERS	Nausea
GASTROINTESTINAL DISORDERS	Vomiting
GENERAL DISORDERS AND	Other, specify (asthenia)

THIS PROTOCOL IS FOR RESEARCH PURPOSES ONLY, SEE PAGE 1 FOR USAGE POLICY

ADMINISTRATION SITE CONDITIONS	
GENERAL DISORDERS AND ADMINISTRATION SITE CONDITIONS	Fatigue
GENERAL DISORDERS AND ADMINISTRATION SITE CONDITIONS	Peripheral edema
INFECTIONS AND INFESTATIONS	Other, specify
INFECTIONS AND INFESTATIONS	Sepsis
INVESTIGATIONS	Creatinine increased
INVESTIGATIONS	Weight loss
METABOLISM AND NUTRITION DISORDERS	Anorexia
METABOLISM AND NUTRITION DISORDERS	Dehydration
METABOLISM AND NUTRITION DISORDERS	Hyperglycemia
METABOLISM AND NUTRITION DISORDERS	Hypokalemia
METABOLISM AND NUTRITION DISORDERS	Hypomagnesemia
METABOLISM AND NUTRITION DISORDERS	Hyponatremia
NERVOUS SYSTEM DISORDERS	Dizziness
NERVOUS SYSTEM DISORDERS	Dysgeusia
NERVOUS SYSTEM DISORDERS	Headache
NERVOUS SYSTEM DISORDERS	Insomnia
PSYCHIATRIC DISORDERS	Confusion
RESPIRATORY, THORACIS AND MEDIASTINAL DISORDERS	Dyspnea

As referenced in the CTEP Adverse Events Reporting Requirements, an AE that resolves and then recurs during a subsequent cycle does not require CTEP-AERS reporting unless (1) the Grade increases; or (2) hospitalization is associated with the recurring AE.

